14.3 Vital Signs, Height, Weight and BMI

Vital signs, height (as measured by a stadiometer) and weight are assessed at Baseline, at all scheduled visits from Week 2 through Week 52, and at unscheduled visits. BMI will be derived as Weight (kg)/ [Height (m)]².

Vital signs, height, weight and BMI will be summarized using descriptive statistics at Baseline and all scheduled post-baseline visits. The change from Baseline values will also be summarized by cohort at the scheduled post-baseline visits.

Vital sign and weight values will be considered PCI if they meet both the observed value criteria and the change from baseline criteria listed in [Table 5](#). The number and percentage of subjects with post-baseline PCI values will be summarized by cohort at each post-baseline visit and for overall post-baseline. For the overall post-baseline summaries, all post-baseline values will be considered, including unscheduled and out of window values. Subjects with multiple PCI values for a given parameter will be counted only once for that parameter. For the by-visit summary, the numerator for the percentage is the number of subjects with a post-baseline PCI value for the given parameter, visit and cohort, and the denominator is the number of subjects with non-missing values for the given parameter, visit and cohort. For the overall post-baseline summary, the numerator for the percentage is the number of subjects with at least one post-baseline PCI value for the given parameter and cohort, and the denominator is the number of subjects with at least one post-baseline value for the given parameter and cohort. A listing of all subjects with any PCI values will be provided.

Table 5 Criteria for Potentially Clinically Important Vital Signs

Vital Sign Parameter	Unit	Criteria ^a		
		Observed Value	And/Or	Change Relative to Baseline
Systolic blood pressure (supine or sitting)	mmHg	≥140	And	Increase of ≥20
		≤70	And	Decrease of ≥20
Diastolic blood pressure (supine or sitting)	mmHg	≥90	And	Increase of ≥15
		≤50	And	Decrease of ≥15
Pulse (supine or sitting)	bpm	≥120	And	Increase of ≥15
		≤50	And	Decrease of ≥15
Weight	kg	Not Applicable		Increase of ≥7% Decrease of ≥7%

^a A post-baseline value is considered as a PCI value if it meets both criteria for observed value and change from baseline.

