#### **6.4.2 Vital Signs**

Vital signs will include body temperature, resting respiration rate, sitting (or supine) systolic and diastolic blood pressure, and pulse rate. The sitting (or supine) blood pressure should be measured after the subject has been sitting (or supine) for  $\geq 3$  minutes. If the initial blood pressure measurement is:

- $\geq 90$ th percentile systolic and/or diastolic for gender-specific age and height charts from the National Heart and Lung Institute (NHLI) for subjects under 13 years or
- $\geq 120$  mmHg systolic or  $\geq 80$  mmHg diastolic for subjects 13 through 17 years,

at least 5 minutes rest should be allowed after the first measurement; then two additional blood pressure measurements are to be performed consecutively. The average of the three blood pressure measurements, systolic and diastolic, is the final blood pressure measurement and this average is the one to be entered into the EDC. All of the three blood pressure measurements with documentation of the time starting the resting and the time at which the two additional blood pressures are measured should be source documented.

If the subject is reporting symptoms of orthostatic hypotension when standing up after the blood pressure measurement, then the subject will be asked to lie down for 5 minutes, blood pressure and pulse rate will be measured, then the subject will be asked to stand and blood pressure and pulse rate measurements will be repeated after standing 1 to 3 minutes in order to measure the severity of the orthostatic hypotension. Vital signs will be collected at Baseline, at all visits from Week 2 through Week 52, and at unscheduled visits.

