12.5 Examination of Subgroups

Summaries of the change from Baseline in the ABC-I subscale scores will be presented by subgroups below:

- age group (5 through 12 years old or 13 through 17 years old) as stratified in antecedent study
- sex (male or female)
- primary race (white or non-white)
- IQ from antecedent study (<70 or ≥ 70)
- region (US. or rest of world) as stratified in antecedent study
- severity of ABC-I at antecedent study entry (<25 or ≥ 25)
- severity of ABC-Lethargy at antecedent study entry (ABC-L) (<20 or ≥ 20)

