13 METHODS OF EFFICACY ANALYSES

13.1 Analysis of Continuous Efficacy Endpoints

Descriptive statistics for all secondary and exploratory efficacy endpoints listed in Section 12.1 will be tabulated by cohorts based on the double-blind treatment group at scheduled timepoints.

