14.5.2 Tanner Staging

The Tanner staging at Baseline, Week 12, Week 28, Week 44, and Week 52 will be summarized in a frequency table by gender, category (Breast development [female] or Genitalia [male], and Pubic Hair Development) and visit.

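### SAP 14.3 has no age- and sex-standardised weight or BMI summary, so over 52 weeks in 5- to 17-year-olds the 7% weight-increase flag can include normal growth at late visits and in the overall count (cheap improvement).

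*SAP*

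**What the plan says.** On body size, SAP 14.3 states: "Vital signs, height, weight and BMI will be summarized using descriptive statistics at Baseline and all scheduled post-baseline visits". It then adds: "The change from Baseline values will also be summarized by cohort at the scheduled post-baseline visits". BMI is weight in kilograms divided by squared height in metres, with no adjustment for age or sex.

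Table 5 of the SAP, like Protocol Appendix F, sets a weight criterion of "Increase of ≥7" percent or an equal decrease. Blood pressure and pulse must also pass an absolute threshold. Weight has none, so change from Baseline alone decides. The flag is counted at each post-baseline visit and overall, and for the overall count: "For the overall post-baseline summaries, all post-baseline values will be considered, including unscheduled and out of window values". SAP 5.3.2 fixes Baseline as the last value before the first open-label dose.

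Three other provisions bear on the point:

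- **Cohort.** The only definition is in SAP 13.1, where efficacy results "will be tabulated by cohorts based on the double-blind treatment group at scheduled timepoints". Every cohort receives open-label pimavanserin.
- **Age groups.** The split by age in SAP 12.5 has a narrow scope: "Summaries of the change from Baseline in the ABC-I subscale scores will be presented by subgroups below".
- **Maturation.** Under SAP 14.5.2, Tanner stage "will be summarized in a frequency table by gender, category" and visit. It is not linked to weight.

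Neither document defines a weight, height or BMI z-score, a percentile, or any comparison with a growth reference.

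**The concern.** A fixed percentage change from a fixed baseline suits adults, whose expected weight change over a year is near zero. Children and adolescents are expected to gain weight. The longer the follow-up, the more of the flagged increases may be ordinary growth, and the overall count takes in the late visits. No untreated arm runs alongside to show how much growth to expect.

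This matters because the primary objective is long-term safety. Protocol 1.1.2 singles out weight gain as a drawback of the two approved drugs, Protocol 1.1.3 describes adult experience with pimavanserin as showing little or no weight effect, and Protocol 6.4 lists weight gain for active monitoring. A crude Week 52 rate could make a weight-neutral drug look unfavourable, or let a real excess be put down to growth.

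**Working it through.** The plan states no expected rate for the weight flag, so there is no figure of its own to reproduce. The check asks how much growth is needed to trigger the flag.

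**Inputs from the documents:** the 7% criterion (SAP Table 5; Protocol Appendix F); visits at Weeks 12, 20, 28, 36, 44 and 52; age 5 through 17 at antecedent entry, and total exposure of up to 58 weeks (Protocol 3.1).

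**Assumed inputs:** body heights, body weights above the 15 kg entry minimum, growth rates, the shape of growth (linear or compound), and any rise of reference BMI with age. The documents give none of these.

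**Step 1: height growth that triggers the flag at unchanged BMI.** Weight is then proportional to height squared, so the requirement is sqrt(1.07) − 1 = 3.44%. That is 3.8 cm at an assumed 110 cm, 4.8 cm at 140 cm and 5.8 cm at 170 cm.

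**Step 2: allowing for BMI that rises with age.** If expected BMI rises by a fraction d over the year, the requirement is sqrt(1.07/(1 + d)) − 1.

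- d = 0: 3.44% (4.8 cm at 140 cm)
- d = 2%: 2.42% (3.4 cm)
- d = 4%: 1.43% (2.0 cm)

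**Step 3: annual weight growth that alone reaches 7% by week w.** Linear: 7 × 52/w. Compound: 1.07^(52/w) − 1.

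| Week | Linear, % per year | Compound, % per year |
|---|---|---|
| 12 | 30.3 | 34.1 |
| 20 | 18.2 | 19.2 |
| 28 | 13.0 | 13.4 |
| 36 | 10.1 | 10.3 |
| 44 | 8.3 | 8.3 |
| 52 | 7.0 | 7.0 |

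The two forms differ early and agree late. Either way, growth matters little at Week 12 and most at the end.

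**Step 4: dependence on body size.** Weeks to reach the flag = 0.07 × weight ÷ (kg per year) × 52. At an assumed 2 kg per year, a 20 kg child crosses at 0.07 × 20/2 × 52 = 36.4 weeks. A 70 kg adolescent would need 0.07 × 70/2 × 52 = 127.4 weeks, which is beyond the study.

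**Step 5: the opposite direction.** If weight stays flat while height grows 3.44%, the weight change is 0% and BMI changes by 1/1.07 − 1 = −6.5%. Neither weight flag fires, and BMI has no flag.

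**Step 6: age span a reference must cover.** A subject just under 18 at antecedent entry can reach about 18 + 58/52 = 19.1 years.

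**The case against.** The study is descriptive, without hypothesis tests, and a flag for potential importance is not meant to be specific. The plan also holds several partial offsets:

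- Raw height and BMI, with change from Baseline, are tabulated at every scheduled visit. SAP 5.1 includes the minimum and maximum, so extreme individual changes are visible.
- Subjects with flagged values are listed, and collected data are listed unless otherwise specified.
- Weight gain can be reported as an adverse event.
- SAP 5.1.1 also reports change from the antecedent Baseline across both studies. With cohorts defined by double-blind group, this may allow a comparison with placebo, but only over the 6-week double-blind period.

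All of this stands, and it keeps the point small. None of it standardises for age and sex over 52 weeks. SAP 1 places table specifications in a separate document, so an age-group display or a table note might be there; a derived variable and its growth reference belong in the SAP.

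Three stronger readings are tempting, and the documents do not support them:

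- **That a large or known share of flags will be growth.** No growth rates are given, and Step 4 shows that slow-growing older adolescents may never reach the flag through growth alone.
- **That the plan can separate growth from excess gain only at group level.** The minimum and maximum statistics and the listings give some individual information, including on the flat-weight case in Step 5.
- **That the plan is inconsistent because it uses paediatric charts for blood pressure.** Those charts govern eligibility and repeat measurement. Table 5 applies fixed blood-pressure cut-offs at all ages, so the analysis treats the two alike.

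**Conclusion.** The point holds as a cheap improvement. With only raw measures and a change-only 7% flag, the increase rate at late visits and overall can include normal growth. The thresholds are modest: 3.44% in height at constant BMI, or 7.0% in weight over the year. Early visits are little affected, since reaching the flag by Week 12 needs about 30% to 34% a year.

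The absence of a standardised measure, and the arithmetic on the 7% criterion, are firm. The centimetre figures rest on assumed heights, the visit figures on an assumed growth shape, and the 2% and 4% cases on assumed BMI drift. How many subjects are affected cannot be derived from the documents. No planned result is wrong, and standardised scores would aid interpretation without isolating a drug effect.

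**What to change.** In SAP 14.3, keep the raw tables and the 7% flag unchanged, and add:

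1. By-visit summaries of weight, height and BMI z-scores and of change in z-score, standardised for age and sex, by cohort and overall. Use age at each assessment, from birth date or the most precise age recorded, and one pre-specified growth reference and version covering ages 5 to about 19.
2. These summaries and the 7% flag by the antecedent-study age strata (5-12 and 13-17 years).
3. A table note that the increase flag can include normal growth, and that z-scores compare with a reference population and do not replace a control arm.

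The cost is SAP wording, a reference lookup, programming and extra table rows. Stadiometer height and weight are already collected at every treatment visit, and sex is recorded. SAP 8.1 specifies age only at the open-label Baseline visit, so the sponsor should confirm that birth date or an equivalent is available; whole-year age would make the scores less precise. The growth charts cited under Protocol Table 6-2 are stature- and weight-for-age and support only the blood-draw limits, so a reference that includes BMI must still be chosen. Any single reference may fit some of the approximately eight countries less well.

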14.4 Electrocardiogram (ECG)

12-lead electrocardiograms are performed at Baseline, Week 2, Week 6, Week 12, Week 20, Week 28, Week 36, Week 44, and Week 52 visits.

All tracings will be evaluated by a central reading laboratory. At the Baseline visit, the machine-read results will also be recorded. All data, including the machine-read Baseline results, will be listed. ECG data summaries will be performed using the centrally evaluated data.

Observed values of ECG variables (heart rate, PR interval, RR interval, QRS interval, QT interval, and QTc intervals) and the changes from baseline at each assessment timepoint will be summarized. QTc intervals include QTcB (Bazett's formula) and QTcF (Fridericia's formula).

QTcF will also be categorized into the following categories (msec) and the number and percentage of subjects in each category will be summarized at each visit and for the overall post-baseline maximum:

- Observed: ≤450, 451 to 480, 481 to 500, and >500
- Change from Baseline: ≤10, 11 to 30, 31 to 60, and >60

For cardiologist's interpretations, the number and percentage of subjects with ECG results that are determined as normal or abnormal will be summarized at scheduled visits. The overall post-baseline worst interpretation will also be summarized (i.e. if a subject has one or more post-baseline ECG results that is/are considered as abnormal, this subject will be counted in the abnormal category). Cardiologist's interpretations will also be summarized in a shift table to determine the number and percentage of subjects with ECG results classified as normal or abnormal at scheduled post-baseline visits relative to the same classification at the Baseline visit. The shifts from Baseline to overall post-baseline worst interpretation will also be presented. For the by-visit shift summary, the denominator is the number of subjects with non-missing cardiologist's interpretation at Baseline and the given visit for the given cohort. For the summaries of shift from Baseline to the overall post-baseline worst interpretation, the denominator is the number of subjects with non-missing Baseline and at least one post-baseline cardiologist's interpretation for the given cohort.

Electrocardiogram variable values will be considered as PCI values if they meet or exceed the upper limit values listed in Table 6. The number and percentage of subjects with post-baseline PCI values will be summarized at each post-baseline visit and for overall post-baseline. For the by-visit summary, the numerator for the percentage is the number of subjects with a post-baseline PCI value for the given parameter, visit and cohort, and the denominator is the number of subjects with non-missing values for the given parameter, visit and cohort. For the overall post-baseline summary, the numerator for the percentage is the number of subjects with at least one post-baseline PCI value for the given parameter and cohort, and the denominator is the number of subjects with at least one post-baseline value for the given parameter and cohort. A listing of all subjects with any PCI values will be provided.

Table 6 Criteria for Potentially Clinically Important ECG Values

ECG Parameter	Unit	High PCI Criteria
QRS Interval	msec	≥120
PR Interval	msec	≥220
QTcB or QTcF	msec	>500
QTcB or QTcF: change from baseline	msec	>60

14.5 Physical Examination and Tanner Staging

Physical examination and Tanner Staging is performed at Baseline, Week 12, Week 28, Week 44, and Week 52 visits.

14.5.1 Physical Examination

Physical examination results (normal, abnormal, and not done) at Baseline, Week 12, Week 28, Week 44, and Week 52 will be summarized in a frequency table by cohort, body system and visit.

A listing of physical examination data will be provided.

14.5.2 Tanner Staging

The Tanner staging at Baseline, Week 12, Week 28, Week 44, and Week 52 will be summarized in a frequency table by gender, category (Breast development [female] or Genitalia [male], and Pubic Hair Development) and visit.

14.5.3 Syncope and somnolence

Syncope and somnolence are assessed at all scheduled visits from Week 2 through Week 52, and at unscheduled visits. Occurrences syncope and somnolence should be reported as adverse events.

Assessment of syncope and somnolence at each visit will be listed. Incidences of syncope and somnolence during the study will be summarized as TEAEs.

14.6 Other Safety Variables

14.6.1 Columbia-Suicide Severity Rating Scale (C-SSRS)

The C-SSRS will be assessed at all scheduled and unscheduled visits. The number and percentage of subjects with suicidal ideation or behavior during the study (post-Baseline) will be tabulated.

For purposes of calculating percentages, the denominator will be the number of subjects within each cohort with at least one post-Baseline C-SRRS.

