### ***CNS, Psychiatric, and Illicit Drug Use Criteria***

2. Requires treatment with a medication prohibited by the protocol, including concomitant psychotropic drugs targeting irritability, including those used off-label (clonidine, guanfacine, and propranolol; lithium, valproate), medications that prolong the QT interval; and strong cytochrome P450 (CYP) 3A4 enzyme (CYP3A4) inhibitors and inducers (see [Appendix A](#) and [Appendix B](#))
3. Is at a significant risk of suicide, or is a danger to self or others, in the opinion of the Investigator based upon all available sources of information including C-SSRS (positive answer to suicidal ideation questions 4 or 5 [or positive answer to suicidal behavior questions at Baseline])
4. Is at risk of significant violent behavior to the extent that participation would pose an undue risk to other patients, caregivers, or others in the opinion of the Investigator
5. Has a positive urine drug test at Baseline. For study eligibility, the urine toxicology (drug) screen (UDS) must be negative for any substance for which the subject does not have a valid prescription.

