### **6.3 Safety Scales**

#### **6.3.1 Columbia–Suicide Severity Rating Scale**

The C-SSRS monitors changes in suicidal thinking and behavior over time, in order to determine risk ([Posner et al. 2011](#)). The following four constructs are measured: the severity of ideation, the intensity of ideation, behavior, and lethality.

The C-SSRS will be used to assess suicidal ideations and behaviors; the Since Last Visit version will be administered at Baseline, and at all subsequent visits. The C-SSRS results for each subject should be reviewed by the Investigator at each visit. If at any time the C-SSRS results for a given subject reveal potential suicidality, then the Investigator should assess the clinical significance of such results. If a clinically significant risk of suicidality is identified for a subject, then the Investigator should discontinue the subject and implement appropriate treatment ([Sections 4.4 and 3.1.2](#)).

The C-SSRS will be administered at Baseline, at all visits from Week 2 through Week 52, and at unscheduled visits.

The same rater or clinician should perform the C-SSRS together with the same caregiver throughout the study as established at Baseline visit.

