5.2.7 Columbia-Suicide Severity Rating Scale (C-SSRS)

The C-SSRS will be administered at Baseline and at all visits from Week 1 through Week 52, and at unscheduled visits. The C-SSRS monitors changes in suicidal thinking and behavior over time,

in order to determine risk ([Posner et al. 2011](#)). Four constructs are measured: the severity of ideation, the intensity of ideation, behavior, and lethality.

There are 5 questions about suicidal ideation, representing 5 types of suicidal ideation: wish to be dead; non-specific active suicidal thoughts; active suicidal ideation with any methods (not plan) without intent to act; active suicidal ideation with some intent to act, without specific plan; active suicidal ideation with specific plan and intent. If a subject/caregiver answers “yes” to any of these 5 questions, this subject will be counted as having suicidal ideation.

There are 5 questions about suicidal behavior, representing 5 types of suicidal behavior: preparatory acts or behavior; aborted attempt; interrupted attempt; actual attempt; suicide. If a subject answers “yes” to any of these 5 questions, this subject/caregiver will be counted as having suicidal behavior.

Missing C-SSRS item scores will not be imputed.

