5.3.2 Analysis Visit Windows

The Baseline value is defined as the most recent non-missing value collected prior to the administration of the first dose of open-label study drug.

Efficacy and safety assessments will be summarized by analysis visits as presented in [Table 2](#) below.

Table 2 Analysis Visit Windows

Open-label (OL) Analysis Visit Name	Target Study Day ¹	Study Day Interval
OL Baseline	1	≤ 1
OL Week 2	15	2 to 28
OL Week 6	43	29 to 63
OL Week 12	85	64 to 112
OL Week 20	141	113 to 168
OL Week 28	197	169 to 224
OL Week 36	253	225 to 280
OL Week 44	309	281 to 336
OL Week 52	365	≥ 337

¹ If the assessment date \geq first OL dose date, study day = assessment date - first OL dose date + 1, otherwise study day = assessment date – first OL dose. Study day 1 is the first OL dose date.

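### The planned C-SSRS table cannot separate new or worsened suicidality from ideation continuing from Baseline, and it shows no ideation level

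*SAP*

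**What the plan says.** **Summary.** SAP 14.6.1 plans this: "The number and percentage of subjects with suicidal ideation or behavior during the study (post-Baseline) will be tabulated". For the percentage, "the denominator will be the number of subjects within each cohort with at least one post-Baseline C-SRRS", so Baseline status does not enter. Protocol 9.5.2 plans the same summary.

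**Counting rule.** Under SAP 5.2.7, a yes "to any of these 5 questions, this subject will be counted as having suicidal ideation". Behavior is handled the same way. That section also says what the instrument collects: "Four constructs are measured: the severity of ideation, the intensity of ideation, behavior, and lethality".

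**Baseline and recall.** Under Protocol 6.3.1, "the Since Last Visit version will be administered at Baseline, and at all subsequent visits". SAP 5.3.2 defines Baseline in general: "The Baseline value is defined as the most recent non-missing value collected prior to the administration of the first dose of open-label study drug". The Baseline disease characteristics in SAP 8.2 do not include the C-SSRS.

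**Entry.** Exclusion criterion 3 (Protocol 4.2) concerns significant suicide risk in the Investigator's opinion, drawing on all sources. From the C-SSRS it names a "positive answer to suicidal ideation questions 4 or 5" and any positive suicidal behavior answer at Baseline. Types 1-3 are not named.

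**The concern.** The study is uncontrolled, runs for 52 weeks in children and adolescents, and has safety as its primary objective. The C-SSRS is a listed safety evaluation. With no comparator arm, each subject's own Baseline is the main internal reference.

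The planned count does not use that reference. A subject with the same type 1 ideation before and after the first open-label dose adds one to the numerator. So does a subject with none at Baseline who later reports ideation with plan and intent. A subject who moves from type 1 to type 4 or 5 adds no more than type 1 alone would have added. A reader of the table could not say how many subjects became suicidal, or became more so, during open-label treatment.

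**Working it through.** **1. How the SAP treats other safety measures**

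| Measure | Related to Baseline in a summary? |
|---|---|
| Laboratory values (14.2.1.2, 14.2.1.3) | Yes: shift tables; clinically important values split by Baseline status |
| Vital signs and weight (14.3) | Yes: change from Baseline |
| ECG interpretation (14.4) | Yes: shift table, by visit and to worst |
| ESRS-A (14.6.2) | Yes: change from Baseline |
| C-SSRS (14.6.1) | No |

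The two-baseline rule in SAP 5.1.1 covers continuous measures only, so the C-SSRS falls outside it.

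**2. What a counted yes means**

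With Since Last Visit recall, a yes at a post-Baseline visit refers to the time since the previous visit. Ideation present only before Baseline is not counted. The one leak is small: the first dose is taken the day after the Baseline visit (Protocol 5.1.3), so the first post-Baseline interval includes a short pre-dose gap. What the count lacks is a split into new, worsened and continuing.

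**3. Illustration of size**

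The documents give no C-SSRS rate. Their only related figure is the Rule of Three limit in SAP 3.5: 3/193 = 1.55%, stated as 1.6%. It reproduces, and this point does not depend on it.

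Inputs:
- N = 193 (SAP 3.5). I assume all 193 have a post-Baseline C-SSRS.
- b = share with ideation at Baseline, assumed 1% to 10%.
- q = share of those who report it again, assumed 0% to 100%.
- e = new-onset rate among subjects without Baseline ideation, assumed 1% to 3%.

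Formulas: continuing = N × b × q; new = N × (1 − b) × e; counted = continuing + new.

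Scenario A in full: 193 × 0.05 × 0.5 = 4.83; 193 × 0.95 × 0.01 = 1.83; sum 6.66; 6.66/193 = 3.45%; 4.83/6.66 = 72%.

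| Scenario | b | q | e | Continuing | New | Counted | Counted, % of 193 | Continuing share |
|---|---|---|---|---|---|---|---|---|
| A | 5% | 50% | 1% | 4.83 | 1.83 | 6.66 | 3.45% | 72% |
| B | 1% | 50% | 3% | 0.97 | 5.73 | 6.70 | 3.47% | 14% |
| C | 5% | 100% | 1% | 9.65 | 1.83 | 11.48 | 5.95% | 84% |
| D | 10% | 100% | 1% | 19.30 | 1.74 | 21.04 | 10.9% | 92% |
| E | 5% | 0% | 1% | 0 | 1.83 | 1.83 | 0.95% | 0% |

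A and B would look the same in the planned table, at about 6.7 subjects each, although B has about three times as many new cases (5.73/1.83 = 3.1). If nothing persists (E), the count contains only new cases.

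**4. Severity level**

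This part needs no rates. With five types reduced to yes/no, a subject at type 1 and a subject at type 5 both contribute one, so the table cannot show movement between them.

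**The case against.** - **The counted events did happen during the study.** This stands. A reader might infer that ideation from before dosing is reported as occurring on open-label drug. The Since Last Visit version rules that out, apart from the short pre-dose gap.
- **The Baseline C-SSRS is used.** This also stands in part. It feeds exclusion criterion 3, and SAP 5.1 lists all data captured in EDC unless otherwise specified. It would be wrong to say that the Baseline assessment is never used; it is absent from the summary tables. A listing does not supply a prespecified count of emergent or worsened subjects.
- **Entry is restricted by more than a question number.** True. Exclusion 3 draws on all sources, and inclusion criterion 4 requires clinical stability and no imminent suicide risk. Both rest on Investigator opinion and leave room for types 1-3.
- **Escalation can surface as an adverse event.** Worsening in severity starts a new event (Protocol 7.2.3), and TEAEs are summarized by maximum severity, seriousness and discontinuation (SAP 14.1). Coverage is partial, because the documents do not require every C-SSRS yes to be recorded as an adverse event.
- **Table shells sit in a separate document** (SAP 1) and may show rows by type. Possibly, but a Baseline comparison that the SAP does not define cannot be assumed.
- **Any-yes counting over-includes rather than misses subjects.** True of the total. It does not help a reader who needs to know how many cases are new or worse.
- **An emergent count has its own bias.** This stands and is carried into the fix.

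**Conclusion.** The point holds as a gap in the planned summary. The table in SAP 14.6.1 does not separate emergent or worsened suicidality from ideation continuing from Baseline, and it shows no ideation level. The loss of level follows from the text alone. The mixing of new and continuing cases depends on how many subjects enter with ideation and report it again, which the documents do not state. Over the assumed ranges the continuing share runs from 0% to about 92%, so no single inflation figure should be quoted as a finding.

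The documents do not support the stronger reading that the table moves pre-dose ideation onto open-label drug. Also, before dosing can only mean before open-label dosing: subjects given pimavanserin in the antecedent study are not drug-free at this Baseline.

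The change is worth making because Baseline is the main internal reference and the data already exist.

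**What to change.** In SAP 14.6.1:

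1. Tabulate ideation by type 1-5, and behavior by type, at Baseline and as worst post-Baseline. SAP 5.3.4 already lets extreme-value safety analyses draw on all post-Baseline values.
2. Add a shift table from Baseline to worst post-Baseline with the categories none, ideation 1-3, ideation 4-5 and behavior.
3. Count emergent subjects (none at Baseline, any afterwards), with subjects clear at Baseline and assessed afterwards as the denominator. Count worsened subjects (higher ideation type than at Baseline, or new behavior), with subjects assessed at both as the denominator.
4. As a sensitivity summary, repeat this against antecedent-study C-SSRS data from before the first pimavanserin dose, where available.

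The planned any-yes count can stay as the top line, so the summary in Protocol 9.5.2 is still delivered.

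The cost is a few extra tables and definitions, with no new data collection. The table needs a footnote: Baseline covers one recall interval, while worst post-Baseline covers up to eight scheduled visits plus any unscheduled ones. Intermittent ideation that did not fall in the Baseline interval may therefore be labelled emergent.
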